# Table 7-8. Pharmacokinetic Assessments, TN/U Expansion Cohort

Study 5F9005: A Phase 1b Trial of Magrolimab Monotherapy or Magrolimab in Combination with Azacitidine in Patients with Hematological Malignancies TN/U Expansion Cohort Cycle 1 Cycle 2 C3+ **EOT** SFU 1 7 8 15 22 1 8 1 Day Χ Pretreatment a  $X^b$ Χ Χ Χ Χb Χ Χ Χ Q2Cd 30 min (± 15 min) after end of Χ Χ Χ Χ azacitidine Q2Cd infusion/injectionc 1 hour (± 15 min) Χ

Abbreviations: C = cycle; EOT = end-of-treatment; min = minute(s); PK = pharmacokinetic; Q2C = every 2 cycles; SFU = safety follow-up; TN/U = Treatment-naïve/Unfit.

Note: PK samples are to be collected from the arm opposite from infusion site, or alternatively, infusion site must be flushed with 10 mL of saline.

a. Collect pretreatment specimens within 12 hours prior to study drug administration.

Χ

b. Pretreatment sample to be collected before either study drug (azacitidine or magrolimab) is started.

Χ

Q2Cd

- c. Azacitidine will be given before magrolimab on days on which both treatments are to be given.
- d. Samples to be collected every other cycle beginning with Cycle 3 through Cycle 13. No PK samples will be collected after Cycle 13.

Table 7-9. Pharmacokinetic Assessments, Magrolimab Monotherapy During Azacitidine Hold(s)

Study 5F9005: A Phase 1b Trial of Magrolimab Monotherapy or Magrolimab in Combination with Azacitidine in Patients with Hematological Malignancies

Magrolimab Monotherapy During Azacitidine Hold(s)

	Cycle X					
Day	1	15				
Pretreatment a	X b,c					

Abbreviations: MRD = minimal residual disease; PK = pharmacokinetic; RO = receptor occupancy. Note: PK samples are to be collected from the arm opposite from infusion site.

- a. Collect pretreatment specimens within 12 hours prior to study drug (magrolimab) administration using Cycle 3+ Day 1 kits. Do NOT collect bone marrow, MRD, RO, or correlative studies.
- b. Pretreatment sample to be collected before study drug (magrolimab) is started. Samples to be collected every other cycle beginning with Cycle 3 through Cycle 13. No PK samples will be collected after Cycle 13.
- c. In RBC Transfusion-dependent Low-risk MDS Cohort, samples to be collected every other cycle beginning with Cycle 3 through Cycle 13. No PK samples will be collected after Cycle 13.

Table 7-10. Pharmacokinetic Assessments, RBC Transfusion-dependent Low-risk MDS Cohort

Study 5F9005: A Phase 1b Trial of Magrolimab Monotherapy or Magrolimab in Combination with Azacitidine in Patients with Hematological Malignancies RBC Transfusion-dependent Low-risk MDS Cohort Cycle 1 Cycle 2 **EOT** SFU Cycle 3+ 1 1 8 15 15 1 Day Χ Pretreatment a Χb Χb Χ Χ Χ Χ Q2C-Q3Cd 15 min (± 15 min) after end of Χ magrolimab infusion

Abbreviations: C = cycle; EOT = end-of-treatment; min = minute(s); PK = pharmacokinetic;

Q2C = every 2 cycles; RBC = red blood cell; SFU = safety follow-up.

Note: PK samples are to be collected from the arm opposite from infusion site, or alternatively, infusion site must be flushed with 10 mL of saline.

- a. Collect pretreatment specimens within 12 hours prior to study drug administration.
- b. Pretreatment sample to be collected before either study drug (azacitidine or magrolimab) is started.
- c. Azacitidine will be given before magrolimab on days on which both treatments are to be given.
- d. Samples to be collected every other cycle beginning with Cycle 3 through Cycle 7 and then every third cycle through Cycle 13. No PK samples will be collected after Cycle 13 until EOT and/or SFU.

Table 7-11. CD47 Receptor Occupancy Sample Time Points, R/R Expansion Cohort Note: Cohort Closed to Enrollment

Study 5F9005: A Phase 1b Trial of Magrolimab Monotherapy or Magrolimab in Combination with Azacitidine in Patients with Hematological Malignancies  R/R Expansion Cohort									
Phase 1b	Cycle 1 Cycle 2 C3+ EOT SFU								
Day	1	8	11	15	1	1	-	_	
Pretreatment (or non-treatment day) a	Х	Х	Х	Xp	Xp	X Q2C- Q3C b,c,d	Х	х	

Abbreviations: C = cycle; EOT = end-of-treatment; RO = receptor occupancy; Q2C = every 2 cycles; Q3C = every 3 cycles; R/R = Relapsed/Refractory; SFU = safety follow-up; UK = United Kingdom; US = United States.

Note: RO is a US-only sub-study; RO specimens are not required for UK patients.

- a. Collect pretreatment specimens within 12 hours prior to study drug administration.
- b. Pretreatment sample to be collected before either study drug (azacitidine or magrolimab) is started.
- c. For visits that include bone marrow assessments, RO blood specimen should be collected on the same day as RO bone marrow specimen is collected.
- d. RO blood samples collected on Day 1 of every other cycle during Cycles 3 through 7, then every 3 cycles (same day as bone marrow RO samples) after Cycle 7 through Cycle 13.

Table 7-12. CD47 Receptor Occupancy Sample Time Points, TN/U Expansion Cohort

Study 5F9005: A Phase 1b Trial of with Azacitidine in Patients with He TN/U Expansion Cohort						limab in Co	ombinati	on
Phase 1b	Cycle 1 Cycle 2 C3+ EOT SF							
Day	1	8	11	15	1	1	_	–
Pretreatment (or non-treatment day) a	Xp	х	х	х	Xp	X Q2C- Q3C a,b,c	Х	х

Abbreviations: C = cycle; EOT = end-of-treatment; Q2C = every 2 cycles; Q3C = every 3 cycles; RO = receptor occupancy; SFU = safety follow-up; TN/U = Treatment-naïve/Unfit; UK = United Kingdom; US = United States.

Note: RO is a US-only sub-study; RO specimens are not required for UK patients.

- a. Pretreatment sample to be collected within 12 hours prior to administration of either study drug (azacitidine or magrolimab).
- b. For visits that include bone marrow assessments, RO blood specimen should be collected on same day as RO bone marrow specimen is collected.
- c. RO blood samples will be collected on Day 1 of every other cycle during Cycles 3 through 7, then every 3 cycles (same day as bone marrow RO samples) after Cycle 7 through Cycle 13.

Table 7-13. CD47 Receptor Occupancy Sample Time Points, RBC Transfusion-dependent Low-risk MDS Cohort

Study 5F9005: A Phase 1b Trial of Magrolimab Monotherapy or Magrolimab in Combination with Azacitidine in Patients with Hematological Malignancies RBC Transfusion-dependent Low-risk MDS Cohort										
Phase 1b Cycle 1 Cycle 2 C3+ EOT SFU										
Day	1	8	15	1	1	_	_			
Pretreatment (or non-treatment day) a	Xp	х	х	Xp	X Q2C, Q4C, Q6C a,b,c	Х	Х			

Abbreviations: C = cycle; EOT = end-of-treatment; Q2C = every 2 cycles; Q3C = every 3 cycles; RO = receptor occupancy; SFU = safety follow-up; TN/U = Treatment-naïve/Unfit; UK = United Kingdom; US = United States.

Note: RO is a US-only sub-study; RO specimens are not required for UK patients.

- a. Pretreatment sample to be collected within 12 hours prior to administration of either study drug (azacitidine or magrolimab).
- b. For visits that include bone marrow assessments, RO blood specimen should be collected on same day as RO bone marrow specimen is collected.
- c. For the TN/U Expansion Cohort, RO blood samples will be collected on Day 1 of every other cycle during Cycles 3 through 7, then every 3 cycles (same day as bone marrow RO samples) after Cycle 7 through Cycle 13. For the RBC Transfusion-dependent Low-risk Cohort, RO blood samples (US only) will be collected on Day 1 of every other cycle during Cycles 3 to 7, then every 4 cycles through Cycle 19, and then starting Cycle 23 and onwards every 6 cycles (same day as bone marrow RO samples).

Table 7-14. Re-priming/Re-escalation Assessments: R/R Cohort and TN/U Cohort

	Visit Window											
Assessment	No	ne		± 3 Days								
Cycle Day (Cycle: 28 Days)	1	2	3	4	5	6	7	8	11	15	22	
CBC with differential, platelets, reticulocytes a,b	Х	Х		Х				Х	Х	Х	Х	
Peripheral blood smear a,c	Х	Х						Х		Х		
Serum or plasma chemistry a	Х	Х						Х		Х	Х	
Serum uric acid, phosphorus a	Х	Х						Х		Х		
Haptoglobin, D-dimer, thrombin, fibrinogen a	Х	Х						Х		Х		
PT/INR, aPTT a								Х				
Anti-drug antibodiesd	Х											
CD47 RO blood e	Х							Х	Х	Х		
ECOG a	Х							Х		Х		
Vital signs f	Х	Х						Х		Х		
Physical examination a,g	Х							Х		Х		
Adverse events	_										-	
Concomitant medications	_										-	
Magrolimab premedication	Х			Х				Х	Х			
Magrolimab: Re-priming/re-escalation h	Х			Х				Х	Х	Х	Х	
Azacitidine h,i	Х	Х	Х	Х	Х	Х	Х					

Abbreviations: aPTT = activated partial thromboplastin time; CBC = complete blood count; ECOG = Eastern Cooperative Oncology Group; IV = intravenous; PE = physical examination; PT/INR = prothrombin time/international normalized ratio; Rh = Rhesus factor; RO = receptor occupancy; SC = subcutaneous; US = United States; WBC = white blood cell.

- a. Pretreatment assessments for the initial dose (Cycle 1 Day 1) may be collected up to 72 hours before study drug administration; thereafter, pretreatment assessments are to be collected within 24 hours prior to study drug administration.
- b. Samples for CBC must be collected at least once per cycle. However, CBC sample collection to ensure a WBC level < 20 × 10^3/mcL may be deferred, based on Investigator assessment of the patient's WBC kinetics. Additional samples for CBC may be collected outside of the protocol-specified time points to ensure a WBC level < 20 × 10^3/mcL.
- c. Peripheral smears will be collected prior to selected study drug infusions/injections and assessed for the presence of hemagglutination in addition to standard cell morphology assessment. Details are provided in Section 7.3.3.
- d. Samples to be collected before dose administration (within 72 hours for initial dose and within 24 hours for subsequent doses).
- e. Time point details for RO studies (US-only sub-study) are provided in Table 7-11 and Table 7-12. Note that the ±3 day visit window does not apply to specimen collection for RO assessments.
- f. Vital signs prior to infusion and within 30 minutes after the end of each infusion. Weight at screening and Day 1 of each cycle. Details are provided in Section 7.3.5.
- g. Full PE at screening, symptom-directed PE thereafter. For Cycles 4 and beyond, PEs may be done only on Day 1 of each cycle, at the discretion of the Investigator.
- h. Magrolimab/azacitidine dosing for re-priming/re-escalation is shown in Table 6-1.
- i. For patients on combination therapy, dosing with azacitidine should follow azacitidine 75 mg/m² SC or IV² on Days 1 to 7.

Table 7-15. Re-priming/Re-escalation Assessments: RBC Transfusion-dependent Low-risk MDS Cohort

				Visit W	/indow			
Assessment	None		S a					
Cycle Day (Cycle: 28 Days)	1	2	3	4	5	8	15	22
CBC with differential, platelets, reticulocytes b,c	Х					X	X	Χ
Peripheral blood smear b,d	Х					Χ	X	Χ
Serum or plasma chemistry b	Х					Х	Х	Х
Serum uric acid, phosphorus b	Х					Х	Х	
Haptoglobin, D-dimer, thrombin, fibrinogen b	Х					Х	Х	
PT/INR, aPTTb						Х		
Anti-drug antibodies e	Х							
CD47 RO bloodf	Х					Х	Х	
ECOG b	Х						Х	
Vital signs g	Х					Х	Х	Χ
Physical examination b,h	Х					Х	Х	
Adverse events							-	
Concomitant medications							-	
Magrolimab premedication	Х					Х		
Magrolimab: Re-priming/re-escalation i	Х					Х	Х	Х
Azacitidine i	Х	Х	Х	Х	Х			

Abbreviations: aPTT = activated partial thromboplastin time; CBC = complete blood count; ECOG = Eastern Cooperative Oncology Group; MDS = myelodysplastic syndrome; PE = physical examination; PT/INR = prothrombin time/international normalized ratio; RBC = red blood cell; Rh = Rhesus factor; RO = receptor occupancy; US = United States; WBC = white blood cell.

- a. Note that ± 3-day visit window does not apply to specimen collection for RO assessments.
- b. Pretreatment assessments for the initial dose (Cycle 1 Day 1) may be collected up to 72 hours before study drug administration; thereafter, pretreatment assessments are to be collected within 24 hours prior to study drug administration.
- c. Samples for CBC must be collected at least once per cycle. However, CBC sample collection to ensure a WBC level < 20 × 10^3/mcL may be deferred, based on Investigator assessment of the patient's WBC kinetics. Additional samples for CBC may be collected outside of the protocol-specified time points to ensure a WBC level < 20 × 10^3/mcL.
- d. Peripheral smears will be collected prior to selected study drug infusions/injections and assessed for the presence of hemagglutination in addition to standard cell morphology assessment. Details are provided in Section 7.3.3.
- e. Samples to be collected before dose administration (within 72 hours for initial dose and within 24 hours for subsequent doses).
- f. Time point details for RO studies (US-only sub-study) are provided in Table 7-13.
- g. Vital signs prior to infusion and within 30 minutes after the end of each infusion. Weight at screening and Day 1 of each cycle. Details are provided in Section 7.3.5.
- h. Full PE at screening, symptom-directed PE thereafter. For Cycles 4 and beyond, PEs may be done only on Day 1 of each cycle, at the discretion of the Investigator.
- i. Magrolimab/azacitidine dosing for re-priming/re-escalation is shown in Table 6-1.

# 7.2. Assessments by Study Period

# 7.2.1. Screening Assessments

The following procedures are to be completed during the screening period for the R/R Cohorts and the TN/U Cohorts:

# R/R Cohorts, TN/U Cohorts, and RBC Transfusion-dependent Low-risk Cohort:

- Confirmation that the ICF has been signed and consent process has been documented.
- Confirmation that all inclusion/exclusion criteria have been met.
- Demographic data including sex, date of birth, age, race, and ethnicity.
- Relevant medical and cancer history through Day 1 (first dose of study treatment)
   with all findings recorded on the Medical History eCRF.
- Enrollment cohort assignment
- Urine or serum pregnancy test (in WOCBP).
- Donor chimerism, for patients with prior allogeneic hematopoietic stem cell transplant only (not applicable to the TN/U Cohort or RBC Transfusion-dependent Low-risk Cohort)
- Local laboratory values, including hematology, serum or plasma chemistry, and urinalysis (Table 7-16)
- Local laboratory peripheral blood smears (Section 7.3.3).
- Local laboratory type and screen (ABO/Rh) and DAT (Section 6.2.2.1 and Section 7.3.4).
- Physical examination (complete) and ECOG (Appendix C).
- Vital signs: blood pressure, heart rate, respiration, temperature, height and weight.
- Single electrocardiogram (ECG).
- Bone marrow core biopsy (trephine) and aspirate (within 30 days prior to first dose of drug), with conventional cytogenetic testing per institutional standard and for CD47 RO (US only)/CCI
- MRD monitoring assessments (Section 7.12.3).

- AEs related to screening procedures or protocol-mandated interventions (e.g., AEs related to invasive procedures such as biopsies) and any SAE reporting.
- Documentation of concomitant and prior medications.

For the Rollover Cohort, assessments performed during the previous study (SCI-CD47-002) may be used as baseline values for this study as long as they meet the criteria for this study with respect to timing. Ongoing AEs and concomitant medications from the previous study will be transferred to the database for this study. The following procedures are to be completed during the screening period for the Rollover Cohort:

#### **Rollover Cohort:**

- Confirmation that the ICF has been signed and consent process has been documented.
- Confirmation that all inclusion/exclusion criteria have been met.

Screening assessments will be completed within a 30-day screening period prior to enrollment. Patients may qualify for enrollment at any time during the 30-day screening period. Assessments performed as part of SOC prior to ICF signature may be used if they are within the required screening period.

## 7.3. Description of Study Procedures

Study procedure timing is provided in Section 7.1, Schedule of Assessments tables.

## 7.3.1. Pregnancy Test

Pregnancy tests are required only for female patients of childbearing potential. Note that a woman is considered to be of childbearing potential (WOCBP), i.e., fertile, following the initiation of puberty (Tanner stage 2) until becoming postmenopausal unless permanently sterile or has medically documented ovarian failure. Permanent sterilization methods include hysterectomy, bilateral salpingectomy, and bilateral oophorectomy. Women are considered to be in a postmenopausal state when they are at least 54 years of age with cessation of previously occurring menses for at least 12 months without an alternative medical cause. A high follicle stimulating hormone (FSH) level in the postmenopausal range may be used to confirm a post-menopausal state in women not using hormonal contraception or hormonal replacement therapy.

However, in the absence of 12 months of amenorrhea, a single FSH measurement is insufficient. A urine or serum pregnancy test is required at Screening (except for the Rollover Cohort) and within 72 hours before study drug administration on Day 1. The Day 1 pregnancy test does not need to be repeated if the Screening pregnancy test was performed within the 72 hours before study drug administration. Pregnancy tests will be performed on Day 1 of each cycle.

### 7.3.2. Complete Blood Counts

Samples for CBCs should be collected per the Schedule of Assessments in Section 7.1, and must be collected at least once per cycle. However, CBC sample collection to ensure a WBC level  $\leq 20 \times 10^3$ /mcL may be deferred, based on Investigator assessment of the patient's WBC kinetics. Additional samples for CBC may be collected outside of the protocol-specified time points to ensure a WBC level  $\leq 20 \times 10^3$ /mcL.

All participants must have a documented hemoglobin ≥ 9 g/dL prior to administering the first 2 doses of magrolimab. Participants who do not meet these criteria must be transfused and have their hemoglobin rechecked to meet the minimum hemoglobin threshold prior to administering each of the first 2 doses of magrolimab.

### 7.3.3. Peripheral Blood Smear Assessment

Peripheral smears will be collected prior to selected study drug infusions/injections and assessed for the presence of hemagglutination in addition to standard cell morphology assessment. These samples should be collected from the arm contralateral to the arm being used for drug infusion/injection, if possible. Peripheral smears will be evaluated according to the guidelines provided in Appendix D.

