A second treatment-related effect on erythrocytes is hemagglutination, which is presumed to result from the direct interaction of magrolimab with CD47 on RBCs. Hemagglutination, when present, has been typically observed within 24 hours of study drug administration and is transient and reversible. Although D-dimer elevation was also common, there was no evidence of disseminated intravascular coagulation,

coagulopathy, microangiopathy, thromboembolic disease, or other clinical sequelae associated with the hemagglutination findings. Because RBC agglutination may be related to the early, rapid rise in magrolimab concentration in the blood of treatment-naïve patients, the duration of infusion of the initial two 1 mg/kg priming doses has been extended from 1 to 3 hours (± 30 minutes) in all patients starting in the maintenance dose phase of the solid tumor Phase 1 study. Hemagglutination has been observed in 21 of 36 (58%) patients treated using the 3-hour priming dose infusion. In contrast, hemagglutination was observed in 6 of 6 (100%) previous patients treated with a 1-hour priming infusion (1 mg/kg). The duration of the maintenance dose infusions remains the same at 2 hours starting at Week 2.

Other common treatment-related adverse events (AEs) in solid tumor patients include infusion-related reactions, mild headache, dizziness, fatigue, nausea, photopsia, fever, chills, urine discoloration, mild transient visual changes, low back pain, and abdominal pain. The majority of these findings have occurred following the first infusion, with very few study drug-related toxicities reported beyond the first cycle. Several patients have been treated with consecutive weekly magrolimab therapy for over 6 months without evidence of long-term toxicities.

In the Phase 1 AML trial (SCI-CD47-002), 15 patients have been treated across 5 dose cohorts. In addition, as of 31 December 2017, 10 AML and MDS patients have been treated in the R/R AML Cohort at up to 30 mg/kg of magrolimab in this study. Overall, magrolimab has been well tolerated in patients in both the Phase 1 AML trial (Study SCI-CD47-002) and this Phase 1b trial. An MTD has not been reached. Similar to the solid tumor experience, the main toxicities associated with magrolimab have been RBC-related (specifically anemia and hemagglutination).

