Anemia has been observed throughout magrolimab dosing in AML patients, with an average 1 to 2 g/dL decrease in hemoglobin observed with each dose. Similar to solid tumor patients, a mild transient increase in unconjugated bilirubin has been observed which is consistent with antibody-mediated extravascular hemolysis of RBCs. In contrast to solid tumor patients, AML patients lack adequate bone marrow function.

[figure not shown]
Thus, reticulocytosis post-magrolimab dosing has rarely been observed in the AML patients treated to date. However, RBC and/or platelet transfusions have been well-tolerated in all AML patients treated with magrolimab. Patients have been able to be successfully typed and crossmatched and have had no adverse safety findings during RBC transfusions while on magrolimab therapy. RBC transfusion frequencies have generally been consistent with transfusion requirements typically observed in AML patients.

Hemagglutination on peripheral smear has been observed at multiple time points and generally occurs post-magrolimab dosing in AML patients. Similar to the solid tumor experience, there has been no evidence of associated disseminated intravascular coagulation, treatment-related thrombocytopenia, coagulopathy, microangiopathy, thromboembolic disease, or other clinical sequelae associated with the hemagglutination findings. A 3-hour infusion duration of magrolimab for doses 1 mg/kg or less was used to potentially reduce frequency of hemagglutination, as observed in the solid tumor trial. In contrast to the experience in solid tumor patients, hemagglutination has been observed across multiple time points, which is likely due in part to ongoing RBC transfusions that contain a fraction of untreated, aged RBCs that are still susceptible to magrolimab-mediated clearance and agglutination. Lastly, mild infusion-related reactions manifested as fevers, chills, headache, and pain, have been observed in a less than 10% of patients during the initial first several doses of magrolimab. Apart from these expected toxicities, magrolimab treatment has been well tolerated in AML patients with no other significant treatment-related toxicities observed.

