# 6.2. Dose Modifications, Dose Delays, and Safety Management Guidelines

# 6.2.1. Dose Modification and Delay Guidelines

## 6.2.1.1. Magrolimab

## **Dose Modifications**

Magrolimab may be withheld if treatment-emergent and/or magrolimab-related AEs occur, which include all AEs that constitute a DLT, as defined in Section 3.3.5.

Magrolimab may be reintroduced at a 50% dose reduction if the severity has recovered to Grade  $\leq$  2 within 4 weeks and in the absence of disease progression, with approval from the Medical Monitor. A dose delay for up to 3 days may be permissible if the patient's WBC count is greater than 20 × 10 $^9$ /L (which is applicable to Cycle 1), to allow for oral hydroxyurea or etoposide treatment to reduce the WBC count. Further dose delay due to elevated WBC counts must be discussed and approved by the Medical Monitor.

Patients who experience a Grade 4 or higher AE of hemagglutination and/or microangiopathy related to magrolimab will permanently discontinue magrolimab treatment. Patients who experience Grade 3 hemagglutination and/or microangiopathy will have magrolimab dosing withheld, and may be reintroduced at a 50% dose reduction if the event severity recovers to Grade  $\leq$  1 within 4 weeks and there is no evidence of disease progression.

With one exception, patients who experience a DLT will have their treatment held for up to 4 weeks to allow sufficient time for recovery, but may restart dosing at a lower dose level if they still meet study eligibility criteria. Patients who experience a DLT of Grade 4 non-hematological toxicity will not restart magrolimab and will be withdrawn from study drug treatment. Data from patients who restart dosing after the recovery period will not contribute to the MTD evaluation at the lower dose level. Treatment delays of more than 4 weeks (such as for an unrelated medical condition with expected recovery) must be discussed with the Medical Monitor and approved by the Sponsor.

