Cycle Day	sc	1	2	3	4	5	6	7	8	11	15	22	1	2	3	4	5	6	7	8	15	22	1	2	3	4	5	6	7	15
Magrolimab: Expansion Cohort t,w		Х			Х				х	Х	Х	Х	х							Х	Х	Х	Х							Х
Azacitidine v		Х	Х	Х	Х	Х	Х	Х					Х	Х	Х	Х	Х	Х	Х				Х	Х	Х	Х	Х	Х	Х	

Abbreviations: ABO = any of the 4 blood groups A, B, AB, and O comprising the ABO system; ADA = anti-drug antibodies; aPTT = activated partial thromboplastin time; C = cycle; CBC = complete blood count; CTSC = Clinical Trial Steering Committee; DAT = direct antiglobulin test; ECG = electrocardiogram; ECOG = Eastern Cooperative Oncology Group; MIN = minute; MRD = minimal residual disease; PE = physical examination; PK = pharmacokinetics; PT/INR = prothrombin time/international normalized ratio; Q2W = every 2 weeks; Q2C = every 2 cycles; Q3C = every 3 cycles; Rh = Rhesus factor; RO = receptor occupancy; R/R = relapsed/refractory; SC = screening; US = United States; W = week(s); WBC = white blood cell.

- a. Note that ± 3-day visit window does not apply to specimen collection for correlative, PK, or RO assessments in Cycles 1 and 2 refer to Table 7-6, Table 7-7, and Table 7-11 for details.
- b. First dose of magrolimab must be given within 30 days of signing informed consent.
- c. Screening pregnancy test may be used if performed within 72 hours of first dose; pregnancy tests will be conducted on Day 1 of every cycle; additional guidance is provided in Section 7.3.1.
- d. Donor chimerism only applicable to patients with prior allogeneic hematopoietic stem cell transplant.
- e. Pretreatment assessments for the initial dose (Cycle 1 Day 1) may be collected up to 72 hours before administration of either study drug (magrolimab or azacitidine); thereafter, pretreatment assessments are to be collected within 24 hours prior to study drug administration.
- f. Samples for CBC must be collected at least once per cycle. However, CBC sample collection to ensure a WBC level < 20×10³/mcL may be deferred based on Investigator assessment of the patient's WBC kinetics. Additional samples for CBC may be collected outside of the protocol-specified time points to ensure a WBC level < 20×10³/mcL.
- g. Peripheral smears will be collected prior to selected study drug infusions/injections and assessed for the presence of hemagglutination in addition to standard cell morphology assessment. Details are provided in Section 7.3.3.
- h. Time point details for correlative studies are provided in Table 7-6.

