# **AE Severity Grading for Hemagglutination and Microangiopathy**

- Grade 1: Evidence of hemagglutination and/or microangiopathy on peripheral blood smear AND associated clinical sequelae that are asymptomatic or mild, not requiring intervention
- Grade 2: Evidence of hemagglutination and/or microangiopathy on peripheral blood smear AND associated clinical sequelae that require medical intervention
- Grade 3: Evidence of hemagglutination and/or microangiopathy on peripheral blood smear AND associated clinical sequelae that are medically significant, requiring hospitalization or prolongation of existing hospitalization, disabling, or limiting self-care activities of daily living
- Grade 4: Evidence of hemagglutination and/or microangiopathy on peripheral blood smear AND associated clinical sequelae that are life threatening or require urgent intervention
- Grade 5: Evidence of hemagglutination and/or microangiopathy on peripheral blood smear AND associated clinical sequelae that result in death

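### Smears for hemagglutination are timed before dosing although the protocol places the finding after dosing, so only the Cycle 1 Day 2 smear falls about a day after a magrolimab dose

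*Protocol*

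**What the plan says.** Section 7.3.3 fixes both the timing and the purpose of the smears: "Peripheral smears will be collected prior to selected study drug infusions/injections and assessed for the presence of hemagglutination", alongside standard cell morphology. The smear rows of Tables 7-1 to 7-3 also carry a timing footnote. After the initial dose, "thereafter, pretreatment assessments are to be collected within 24 hours prior to study drug administration".

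Section 1.2.2.1 describes when the finding appears. Of solid tumor patients it says: "Hemagglutination, when present, has been typically observed within 24 hours of study drug administration and is transient and reversible". Of AML patients it says: "Hemagglutination on peripheral smear has been observed at multiple time points and generally occurs post-magrolimab dosing in AML patients". It adds that, unlike in solid tumors, "hemagglutination has been observed across multiple time points, which is likely due in part to ongoing RBC transfusions".

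Appendix A has a severity scale for hemagglutination and microangiopathy. All five grades combine a smear finding with clinical sequelae; Grade 2, for example, reads "Evidence of hemagglutination and/or microangiopathy on peripheral blood smear AND associated clinical sequelae that require medical intervention". Section 6.2.1.1 attaches individual treatment rules to the scale. Grade 3 leads to withholding, and for the top of the scale: "Patients who experience a Grade 4 or higher AE of hemagglutination and/or microangiopathy related to magrolimab will permanently discontinue magrolimab".

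Measurement of adverse events by CTCAE or by this customized scale is a primary endpoint (Section 2.2.1).

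**The concern.** The smear schedule looks for a post-dose finding mainly at pre-dose times. If agglutination clears between doses, a sample taken just before the next infusion will tend not to show it. The severity scale cannot be applied without a smear finding, so the timing of smears affects which events can be graded and counted.

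Three things are at stake.

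- **The incidence of hemagglutination**, which is part of a primary endpoint, may be understated.
- **The later, higher doses** are where the schedule is thinnest. The AML text says the finding recurs after later doses, so a smear after the first dose alone does not settle the matter.
- **The 60 mg/kg run-in** in the low-risk MDS cohort exists because that dose had not been tested in MDS patients (Section 3.4). No scheduled smear after a 60 mg/kg dose falls inside its DLT period.

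**Working it through.** The check is a count of nominal days. Dose days come from Tables 3-2 and 3-3 and the drug rows of Tables 7-1 to 7-3. Smear days come from the smear rows of Tables 7-1 to 7-3, and re-priming days from Tables 7-14 and 7-15. Study day = 28 × (cycle − 1) + cycle day. Gap = smear day − last earlier magrolimab dose day. The protocol states no figure of its own to reproduce.

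| Smear | R/R and TN/U Expansion | Low-risk MDS |
|---|---|---|
| C1 D2 | 2 − 1 = 1 day | 2 − 1 = 1 day |
| C1 D8 | 8 − 4 = 4 days | 8 − 1 = 7 days |
| C1 D15 | 15 − 11 = 4 days | no smear |
| C1 D22 | 22 − 15 = 7 days | no smear |
| C2 D1 (day 29) | 29 − 22 = 7 days | 29 − 22 = 7 days |
| C3 D1 (day 57) | 57 − 50 = 7 days | 57 − 29 = 28 days |
| C4 D1 (day 85) and later | 85 − 71 = 14 days | 85 − 57 = 28 days |

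Doses followed by a scheduled smear within one day:

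- R/R and TN/U Expansion, Cycles 1 to 3: 6 + 4 + 2 = 12 doses, of which 1 (8%). Through Cycle 6: 12 + 3 × 2 = 18 doses, of which 1.
- Low-risk MDS, Cycles 1 to 3: 4 + 1 + 1 = 6 doses, of which 1 (17%). Through Cycle 6: 6 + 3 × 1 = 9 doses, of which 1.
- Re-priming cycle: 1 of 6 doses in R/R and TN/U (Day 2). In the low-risk cohort it is 0 of 4, because Table 7-15 has no Day 2 smear.

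In both main schedules the covered dose is C1 D1, at 1 mg/kg.

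Next scheduled smear after the first dose at each higher level:

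- R/R and TN/U, 15 mg/kg (C1 D8): C1 D15, 7 days later, with a further dose in between.
- R/R and TN/U, 30 mg/kg (C1 D11): C1 D15, 4 days later.
- Low-risk, 30 mg/kg (C1 D8): C2 D1, 29 − 8 = 21 days later, with two further doses in between.
- Low-risk, 60 mg/kg (C2 D1): C3 D1, 57 − 29 = 28 days later. The DLT period ends at C2 D15, day 43 (Section 3.4.1), so this smear comes 57 − 43 = 14 days after it has closed.

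The ±3-day visit windows could shorten some gaps in practice. They do not create a planned post-dose smear.

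**The case against.** The case on the other side is substantial, and much of it stands.

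- **Day 2 is a post-dose smear**, so not every smear is pre-infusion. It covers the first dose, and Section 1.2.2.1 links agglutination to the early rapid rise in drug concentration in treatment-naïve solid tumor patients. This stands for the first dose; the AML text says the finding recurs later.
- **The 24-hour, transient description is solid tumor data.** No duration is given for AML or MDS. A reader might infer that events after Day 2 are largely missed. The document does not show that, because how long the finding stays visible in these patients is not stated.
- **Symptomatic patients can still be graded.** A reader might infer otherwise, but nothing forbids an unscheduled smear. Section 6.1.1 asks for further monitoring of patients with treatment-related events during post-infusion observation, and Section 6.2.2.1 asks for further evaluation of severe infusion reactions. Patients at Grade 3 or 4 would present clinically. What remains is that neither provision names a smear, and post-infusion observation is not required after C1 D22, so it does not reach the 60 mg/kg doses.
- **The run-in is judged on DLTs and the aggregate safety profile**, not on routine smears. This is correct. The narrower point is that no scheduled smear after 60 mg/kg can inform that judgement.
- **The rates quoted in Section 1.2.2.1 prove nothing here.** A reader might set 21 of 36 (58%) and 6 of 6 (100%) in solid tumor patients against the 14% reported in this study. The first two are observed agglutination under two infusion durations. The third is a treatment-related adverse event in AML/MDS patients on combination therapy. Population, regimen and definition all differ.
- **Reach is limited.** Tables 7-1 to 7-3 are marked closed to enrollment, so a schedule change cannot recover data on first doses already given.

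**Conclusion.** The point holds as an inconsistency within the protocol. The stated purpose of the smears is to find hemagglutination, the background section places it after dosing, and after C1 D2 no scheduled smear nominally falls within 24 hours after a magrolimab dose. Since Appendix A requires smear evidence at every grade, mild or asymptomatic post-dose hemagglutination is not captured systematically. Confirmation of higher grades depends on unscheduled smears, which may be ordered differently from site to site.

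The likely direction is under-reporting; the size is unknown. That rests on two assumptions: that the finding fades between doses in AML and MDS as it does in solid tumors, and that unscheduled smears do not close the gap. The document establishes neither. The treatment rules concerned act on individual patients and are not trial stopping rules.

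**What to change.** Reconcile Section 7.3.3 and Tables 7-1 to 7-3, 7-14 and 7-15 with Sections 1.2.2.1 and 6.2.1.1 and Appendix A. The grading and treatment rules themselves are not at issue here.

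1. **Add a post-dose smear from draws that already exist.**
   - The hemoglobin check 3 to 6 hours after the start of the first two doses. In the low-risk cohort the second of these is the first 30 mg/kg dose.
   - The 1-hour post-infusion PK samples in R/R and TN/U, including those every 2 cycles from Cycle 3.
   - The 15-minute post-infusion PK sample in the low-risk cohort (Table 7-10). Its visit day could not be read reliably in the text reviewed and should be checked.
2. **Keep the pre-dose smears**, which also serve cell morphology.
3. **Say where a post-dose sample would be new.** This applies to re-priming, since Tables 7-14 and 7-15 have no PK row and the hemoglobin check is limited to initial treatment. It also applies to any 60 mg/kg dose without a post-infusion draw, and to C1 D11 in R/R, for which Table 7-7 has no sample.
4. **In the safety analysis**, report hemagglutination together with the number of doses that had a post-dose smear.

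The cost is a few extra slides, a small number of new samples if item 3 is taken up, and probably a higher observed rate. With enrollment closed, the schedule change helps only patients still on treatment or being re-primed. The reporting statement applies to all.
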